2.3 STUDY OUTCOMES

Aim 1. The primary outcome for aim 1 is satisfaction with the intervention at month 1, assessed by a satisfaction scale. Secondary outcomes are participation in intervention sessions and fidelity to the intervention, assessed via audio-recording. This will be scored with an ACT Adherence Checklist and the Adherence Raters' Manual for Stigma Treatment Study (Kohlenberg et al, 2004) to rate the recorded intervention audio recordings.

[figure not shown]
Aim 2. The primary outcome for aim 2 is measured change in internalized HIV stigma and substance use stigma at 1 and 6 months assessed by the Berger HIV Stigma Scale, the Leickness HIV internalized shame scale, the modified Substance Abuse Self-Stigma Scale, and the Acceptance and Action Questionnaire – Substance Abuse. Secondary outcomes are initiation of ART, recent (last 30 days) injection drug use frequency at 1 and 6 months, and mental health as measured by the PHQ-9 and GAD-7.

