1. INTRODUCTION

1.1 SUMMARY

People who use drugs (PWID) often experience multiple layers of stigma when they are living with HIV.¹ Stigma is defined as the social exclusion and dehumanization of individuals in an undesirable social category.² Interventions to help affected PWID living with HIV cope with the dual stigma related to HIV and substance use have not been studied specifically in this population. Among people living with HIV, stigma adversely impacts all aspects of the care cascade: timely HIV testing, diagnosis, treatment, adherence and retention in care.³⁻⁵ Among PWID, drug use may add to adverse social factors and create particular stigma vulnerability. Russia is a country where PWID and other HIV key populations are highly stigmatized and face discrimination. Furthermore, agonist treatment for opioid use disorder is illegal in the Russian Federation. People with substance use disorders and those living with HIV have to register with the local authorities for treatment. While many try to avoid registration, most PWID and people living with HIV (PLWH) are known to the authorities. Further qualitative findings suggest that in the absence of public anti-stigma campaigns in Russia, stigma reduction interventions should address internalized stigma and their determinants to help affected people cope with the dual stigma. Stigma interventions should be adapted to address not only affected people's shame and guilt, but also their felt hopelessness. These emotions and related feelings such as avoidance and fear of being rejected may negatively affect people's agency and mental health.^{7,8} We are proposing *Acceptance and Commitment Therapy* (ACT) as a potential behavioral intervention to target the emotions underlying internalized stigma and thus empower affected people. ACT has been shown to increase engagement in addiction care.⁹ Its use and efficacy to reduce stigma has not yet been explored among HIV-positive PWID.¹⁰ The objective of this study, "Stigma, Risk Behaviors and Health Care among HIV-positive Russian People Who Inject Drugs (SCRIPT)," is to implement and evaluate the feasibility of an adapted form of ACT targeted to PWID living with HIV in Russia as an intervention to reduce intersectional HIV and substance use stigma via a two-armed randomized controlled trial among 100 HIV-positive PWID. The central hypothesis is that ACT is feasible and can be delivered to decrease HIV and substance use stigma scores.

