3.5 SCHEDULE OF DATA COLLECTION

		Phone Screener	Screener and Baseline		ACT Sessions 1-3	1-month assessment (4 weeks)	6 month visit (24 weeks)
			In-person Screener	Baseline			
Screening	Verification of HIV and hx of IDU	X	X				
	Screening Questions	X	X				
Enrollment	Sign Informed Consent		X				
	Complete contact information/verify numbers			X			
Assessment	Baseline Study Assessment			X			
	1-Month Study Assessment incl ACT satisfaction questions					X	
	6-Month Study Assessment						X
	Interventionist Checklist				X		
Randomization	Randomization			X			
Intervention	Adverse Events			X		X	
	ACT Intervention				X		
Other	Compensate for Participation			X	X	X	X
	Provide Resource Card			X			
	Report Adverse Events			X	X	X	X
	Complete Tracking Forms		X	X	X	X	X

Control Group						
		Phone Screener	Screener and Baseline Visit		1 mo (4 weeks)	6 mo (24 weeks)
			In-person Screener	Baseline		
Screening	Verification of HIV and substance use	X	X			
	Screening Questions	X	X			
Enrollment	Sign Informed Consent		X			
	Complete contact information/verify numbers			X		
Assessment	Baseline Study Assessment				X	
	1-Month Study Assessment					X
	6-Month Study Assessment					X
	Randomization				X	
Other	Provide Resource Card				X	
	Compensate for Participation				X	X

	Complete Tracking Forms			X	X	X
--	-------------------------	--	--	---	---	---

3.5.A. VISIT WINDOWS

ACT Intervention Session Windows for Intervention Group

1st ACT Session

- Window open: 1 day post baseline
- Target date: 7 days post baseline
- Window close: 31 days post baseline
- Window length: 30 days

2nd ACT Session

- Window open: 8 days post baseline
- Target date: 14 days post baseline
- Window close: 29 days post baseline
- Window length: 21 days

3rd ACT Session:

- Window open: 15 days post baseline
- Target date: 21 days post baseline
- Window close: 36 days post baseline
- Window length: 21 days

Research Assessment Windows for Intervention and Control Group

Intervention Group 1 Month (4-week) Visit

- Window open: 16 days post first group session
- Target date: 30 days post first group session
- Window close: 90 days post first group session
- Window length: 74 days

Intervention Group 6 Month (24-week) Visit

- Window open: 151 days post first group session
- Target date: 180 days post first group session
- Window close: 240 days post first group session
- Window length: 89 days

Control Group 1 Month (4-week) Visit

- Window open: 16 days post baseline

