- Target date: 30 days post baseline
- Window close: 90 days post baseline
- Window length: 74 days

Control Group 6 Month (24-week) Visit

- Window open: 151 days post baseline
- Target date: 180 days post baseline
- Window close: 240 days post baseline
- Window length: 89 days

Windows listed above are used as guides for scheduling visits, but deviations may occur due to participant scheduling.

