The ACT stigma intervention will be delivered by clinical psychologists. Supervision will be provided by site PI and an ACT trainer. Interventionists and supervisors will be trained by ACT trainers. To assess interventionist fidelity to ACT, we will use an ACT Fidelity Measure to rate the recorded intervention videos/tapes, with a focus on interventionist behavior and competency. The measure classifies three different targets of clinician behaviors, openness, awareness, engagement, as well as interventionist stance. This will also allow us to investigate how combinations of interventionist behaviors relate to outcomes and help train future interventionists in Russia and Russian speaking countries.

3.6.B MISSED VISITS

The following procedures will take place in the event of an intervention participant missing their group session. If they miss their:

1st session: We will schedule them into the next available group.

2nd session: We will ask them if they would like to participate in an individual make-up session. This will be an adapted session conducted by one of the interventionists who is trained specifically in this individual session. If they choose to not participate in the make-up session, they will still be scheduled for their 3rd session and for their 1-month and 6-month assessments.

3rd session: This will be a missed session, but they will still be invited for their 1-month and 6-month assessments.

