5.2 FOLLOW UP ASSESSMENTS

Phone assessments will be permitted for 6 month assessments, as a last resort, for participants who are unable to come in-person. The 1 month assessment will take about 45 minutes, the final assessment at 6 months will take about 60 min.

Administered Assessment	Baseline	1-Month	6-Month
Demographics	X		
ART Use and Adherence	X	X	X
HIV Sex Risk Behaviors	X	X	X
HIV Risk Categories	X		
HIV Disclosure	X		X
HIV Stigma	X	X	X
Substance Use Stigma	X	X	X
Substance Use Daily Life Experience (SRS)	X		
Acceptance and Action (AAQ-II – SA)	X	X	X
Patient Health Questionnaire (PHQ-9)	X	X	X
Anxiety (GAD-7)	X	X	X
Partner Violence and Sexual Assault	X		
Alcohol Use: AUDIT-C	X		
Perceived Alcohol Stigma	X		
Drug Use	X	X	X
Overdose	X		X
Social Support Scale	X		X
VR-12 Health Survey	X		X
Health Care Utilization	X		X
Abbreviated PTSD Checklist	X		
Involvement with Police	X		X
[‡] Satisfaction with the Intervention		X	
*HIV Testing History	X		
^a COVID-19 testing history, risk behaviors, and perceptions			X

[‡]Intervention group participants only

*If this information is not collected at baseline, RAs will collect this information at a later study visit.

^a Not administered to all 6-month participants

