8. STATISTICAL ANALYSIS

This study will use an intent-to-treat analysis that includes all participants according to their randomized assignment. Descriptive statistics will be calculated for variables at baseline and each follow-up time to assess whether there appear to be any differences across treatment arms.

Our Specific Aims are to compare the effects of SCRIPT and standard of care on following outcomes:

Aim 1: Evaluate the feasibility of an ACT stigma intervention compared to standard of care via a 2-armed RCT of 100 HIV-positive Russian PWID on the following outcomes:

- Primary: Satisfaction with the intervention at 1 month
- Secondary:
 - Participation in three intervention sessions;
 - Fidelity to the intervention, using the Adherence Raters' Manual for Stigma Treatment Study (Kohlenberg et al, 2004) and an intervention adherence score

Aim 2: Measure changes in internalized stigma

Primary:

- a. HIV Stigma via the Simbayi HIV internalized shame scale at 1 month;
- b. Substance Use Stigma via Modified Substance Abuse Self-Stigma Scale at 1 month

Secondary:

- a. Any initiation of HIV care (ART) at 6 months
- b. Engagement in substance use care at 6 months
- c. Change in last 30 days injection drug use at 6 months

Exploratory:

- a. Depression as measured by the PHQ-9 at 6 months
- b. Anxiety as measured by the GAD-7 at 6 months
- c. Intersectional stigma as measured by both substance use stigma and HIV stigma scales at 6 months
- d. Psychological flexibility measured via the Acceptance and Action Questionnaire at 6 months

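### The Aim 1 primary outcome, satisfaction at 1 month, can be observed only in ACT participants who complete that assessment, so neither the promised intention-to-treat analysis nor the named two-sample t-test can be carried out for it

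*Combined protocol and SAP*

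**What the plan says.** Section 2.3 makes satisfaction the Aim 1 primary outcome: "The primary outcome for aim 1 is satisfaction with the intervention at month 1, assessed by a satisfaction scale". Sections 2.1 and 8 repeat this. Feasibility is the first half of the main hypothesis in section 1.1: "The central hypothesis is that ACT is feasible".

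The items sit inside one visit. The ACT schedule in section 3.5 lists "1-Month Study Assessment incl ACT satisfaction questions", and the control schedule has no such entry. The table in section 5.2 marks satisfaction in the 1-month column alone, with the footnote "Intervention group participants only".

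For the ACT arm, section 3.5.A dates that visit from the sessions: "Target date: 30 days post first group session". For controls it is dated from baseline. The section closes with a caveat: "Windows listed above are used as guides for scheduling visits, but deviations may occur due to participant scheduling".

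The missed-visit rules (numbered 3.6.B, printed within section 4.6) give one rule for a missed first session: "1st session: We will schedule them into the next available group". After a missed second or third session, the same rules expressly keep the 1-month assessment.

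On analysis, section 8 says: "This study will use an intent-to-treat analysis that includes all participants according to their randomized assignment". Section 8.1 repeats the intention-to-treat principle, adds allowance for correlation within groups, and names satisfaction scores as the example of a continuous outcome to be compared by two-sample t-test. No section gives the range of the scale, a level that counts as satisfied, or a rule for participants without a score.

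**The concern.** An intention-to-treat analysis needs a defined value, or a rule, for everyone randomised. Here there are three sets of people without one.

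- Controls are never asked.
- ACT participants who never attend have no sessions to rate. Their score is undefined rather than missing, so imputation has no true value to aim at. They also lack an anchored date for the only visit that collects the outcome.
- ACT participants who attend at least once but are not assessed at 1 month have a missing score, and no rule covers it.

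Anyone running the analysis will therefore fall back on a mean among raters. If people who found the sessions unacceptable are less likely to start or to be assessed, that mean flatters the intervention. Non-starting is a realistic possibility: under section 4.5 the first session waits until five ACT participants have been randomised and are available, and section 2.7 requires injection drug use in the past 30 days. At stake is the figure that would be quoted first in support of feasibility.

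**Working it through.** **1. The denominator.** Sections 2.4 and 3.1 give about 13 groups of 5 in the ACT arm: 13 × 5 = 65, and 65 + 35 = 100. The 2:1 ratio in section 3.2 gives 100 × 2/3 = 66.7, which agrees to within 2 participants. So at most 65 of the 100 randomised can have a satisfaction score, and the number of control scores is 0. A two-sample t-test needs scores in both samples, so it cannot be computed. The documents state no satisfaction figure, so there is none to reproduce.

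**2. Who can have a score.**

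| ACT participant | Route to the 1-month assessment | Score |
|---|---|---|
| Misses session 3 | Still invited (missed-visit rules) | Yes, if assessed |
| Misses session 2, declines make-up | Still scheduled (missed-visit rules) | Yes, if assessed |
| Misses session 1, attends a later group | Date counts from that session | Yes, if assessed |
| Never attends a session | No anchor date, no rule beyond rebooking | Undefined |

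**3. Illustration.** Assumed, not in the documents: 52 of 65 give a rating and 44 of them are satisfied. The exact (Clopper-Pearson) limits for x of n are the 2.5% quantile of Beta(x, n − x + 1) and the 97.5% quantile of Beta(x + 1, n − x).

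- Among raters: 44/52 = 84.6%, limits 71.9-93.1%.
- Of all randomised to ACT: 44/65 = 67.7%, limits 54.9-78.8%.

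These limits ignore session grouping, which section 8.1 says must be allowed for.

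With 85% satisfied among raters and a share m without a rating, the all-randomised proportion is 0.85 × (1 − m): 76.5%, 68.0% and 59.5% for m = 10%, 20% and 30%.

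**4. Bounds.** Assumed: about 80% of raters satisfied and 10-40% without a score. With s satisfied among r raters, the worst case is s/65 (no non-rater satisfied) and the best case is (s + 65 − r)/65 (all satisfied).

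| Without a score | Raters satisfied | Worst case | Best case |
|---|---|---|---|
| 10% | 46/58 = 79.3% | 46/65 = 70.8% | 53/65 = 81.5% |
| 20% | 42/52 = 80.8% | 42/65 = 64.6% | 55/65 = 84.6% |
| 30% | 37/46 = 80.4% | 37/65 = 56.9% | 56/65 = 86.2% |
| 40% | 31/39 = 79.5% | 31/65 = 47.7% | 57/65 = 87.7% |

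The raters' figure lies inside each range, so the bounds do not fix the direction of any bias. They do show how quickly the uncertainty grows.

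If non-starters are counted as not meeting the outcome, the upper bound depends on how many of those without a score had attended. In the step 3 illustration, with k attenders among the 13 without a score, it is (44 + k)/65: 67.7% if k = 0 and 57/65 = 87.7% if k = 13.

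**5. Mean score.** The difference between the raters' mean and the full-arm mean is the missing share times the gap between raters and non-raters. If non-raters would score 0.5-1.0 SD lower and 10-40% are missing, the overstatement runs from 0.1 × 0.5 = 0.05 SD to 0.4 × 1.0 = 0.40 SD. This applies only to attenders who were not assessed, because a never-attender has no score to impute.

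**The case against.** The strongest reply is that the plan does much to limit the loss and does not hide it.

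- A reader might infer that people who leave dissatisfied are removed from the figure. The documents do not support that: those who stop after session 1 or 2 are still scheduled for or invited to the 1-month assessment, and a low score from them counts. Only those not assessed are lost.
- A reader might infer that the scale is formally limited to attenders. Section 5.2 limits it to the arm. The exclusion of non-starters follows from the visit anchor and from the nature of the question, and the windows are only guides.
- A reader might infer that the feasibility conclusion cannot fail. Participation in the three sessions and fidelity are separate Aim 1 outcomes, so poor attendance would be seen. No feasibility threshold is stated, but that is a separate matter from who supplies a rating.
- A reader might infer that the raters' figure is biased upward. Upward is the likelier direction, but people may be absent for reasons unrelated to satisfaction; section 7.3 lists an incarceration form.
- Retention measures are substantial: eligibility requires availability at session times (section 2.7), visits and sessions are paid (section 4.7), and no-shows are followed up (section 4.8). Section 4.7 also offers a 1-month assessment by phone as a last resort, although section 5.2 permits phone only at 6 months.
- Satisfaction among those exposed, shown beside attendance, is a legitimate feasibility measure. Counting every non-rater as not satisfied is one bound, not the true value.

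All of this stands, and it limits the claim about bias. It supplies neither control scores for the t-test nor a rule for participants without a score, so the analysis promised in section 8 still cannot be delivered.

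**Conclusion.** The point holds in this form. The Aim 1 primary can be observed only in ACT participants who complete the 1-month assessment, at most 65 of 100. Non-starters have no anchored visit and nothing to rate. The intention-to-treat statement cannot be honoured for this outcome as defined, and the named between-arm test has no second sample. These conclusions rest on the documents alone.

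That a raters-only figure overstates acceptability is plausible but not established. Every rating and non-response rate used above is assumed. In the illustration the headline moves from 85% to 68%; with about 80% of raters satisfied and 20% without a score, the all-randomised range is 64.6-84.6%. The documents cannot say where in such a range the truth would lie.

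**What to change.** In sections 2.3 and 8.1:

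1. Replace the between-arm t-test for satisfaction with a one-arm estimate.
2. Report, with all participants randomised to ACT as denominator, the proportion who attended at least one session and gave a satisfied rating at 1 month, with a 95% CI that allows for session group. Fix the satisfied level in advance.
3. Beside it, show the mean score among raters, the number without a score by sessions attended, and best- and worst-case bounds for those who attended but were not assessed.
4. Base the feasibility statement on the all-randomised figure together with participation, not on the raters' mean alone.

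In section 3.5.A, give ACT non-starters a 1-month date counted from baseline. Reconcile sections 4.7 and 5.2 on whether a 1-month assessment by phone is allowed.

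The cost is mainly wording: attendance and ratings are already planned. The downside is a less favourable headline figure. There is also a timing limit. Randomisation is described in the past tense and COVID-19 arrangements are included, so follow-up may be under way. In that case the satisfied level should be fixed before any satisfaction scores are examined, and the baseline-dated visit can help only non-starters who can still be assessed.

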2.4 STUDY DESIGN

SCRIPT is a Randomized Controlled Trial (RCT) among 100 HIV+ PWID, which aims to test the feasibility of the SCRIPT intervention and evaluate its effectiveness on the reduction of internalized stigma as well as self-reported entry into substance abuse treatment or initiation of ART. Eligible participants will be randomly assigned into one of two groups: 1) Control group receiving CSO site standard of care or; 2) ACT intervention. Both the intervention group and the control group will receive standard of care counseling and referral to addiction treatment and HIV treatment at the CSO sites. Following their baseline assessment, participants assigned to the intervention group will meet with the interventionist three times over one month in approximately 13 groups of 5 people each. All three sessions will be in groups, except for the occasional individual make-up 2nd session (more details in section 3.6B). Study outcomes will be assessed at 1 and 6 months (Figure 1).

Figure 1 illustrates the design of this 2-arm RCT with 65 participants in the SCRIPT intervention arm and 35 participants in the standard of care arm.

Figure: SCRIPT Study Design

Throughout the course of the study, participants in both groups will be expected to participate in three in-person assessments (baseline, 1 month and 6 months).

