2.9 RECRUITMENT GOALS

We aim to randomize 100 participants over 13 months into the trial. We will approach potential participants at CSOs serving PWID and people living with HIV (PLWH) in St. Petersburg.

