3. INTERVENTION

3.1 INTERVENTION OVERVIEW

The study will randomize 100 PWID living with HIV in the St. Petersburg area. We will approach potential participants at CSOs serving PWID and people living with HIV (PLWH). After a phone-screening, potential participants will be given clear transportation instructions to the location of the remainder of the procedures (in-person screening, consent, enrollment, assessments, intervention sessions). After in-person screening, consent, enrollment, and the baseline assessment, participants will be randomly assigned to either the SCRIPT intervention or standard of care. Following randomization, participants in both groups will receive standard of care at the study site.

Following randomization by RAs at the rehabilitation center, participants in the intervention group will be scheduled to engage in group ACT sessions. These will consist of three 2-hour group sessions of culturally adapted ACT to reduce stigma and related manifestations in weeks 1, 2 and 3. The ACT sessions are described in further detail in 3.3.A.

Throughout the course of the study, participants will be expected to participate in three in-person assessments (baseline, 1 month [4 weeks], and 6 months [24 weeks]). Participants in the intervention groups will receive three ACT sessions over one month in approximately 13 groups of 5 people each (n=65), with a final assessment conducted at 6 months.

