3.2 RANDOMIZATION

Randomization is not stratified by any factor. Blocked randomization with randomly selected block sizes was used to reduce selection bias and make the sequence less predictable. We generated a random sequence of 34 blocks, sizes 3 and 6. Then, we randomized assignments within each block with an allocation ratio of 2:1. A greater number of blocks was created than is necessary in the event that the investigator continues enrollment beyond the initially planned sample size. Randomization sequence was created in R, version 3.5.2 (Copyright (C) 2018 The R Foundation for Statistical Computing) and uploaded to REDCap platform, electronic data collection tool.

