4.5 VISIT FLOW

We aim to screen and consent eligible participants, followed by baseline assessment (about 60 minute duration) on the same day. The first ACT group session (about 120 minute duration) will occur once five participants have been randomized into the intervention group and are all available for the pre-scheduled group session. After eligible participants are consented and enrolled, the following will take place at the **Baseline visit**:

- Collection of locator/contact information and verification of contact phone numbers
- Administration of assessment questionnaire
- Randomization
- Compensation and scheduling next visit

Intervention Group:

- Participants randomized into the intervention group will have their group ACT sessions consecutively on weeks 1, 2, and 3.

Intervention and Control Group:

- During the **1-, and 6-month in-person assessments**, the Research Assessor will:
 - Review and update locator/contact information, verifying new numbers, as necessary
 - Administer assessment questionnaire
 - Compensate participant and schedule next visit (1-month visit only)

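### Does the planned 65:35 split in 13 groups of five conflict with 2:1 blocked randomisation of 100 in a way that needs a change?

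*Combined protocol and SAP*

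**What the plan says.** Section 2.9 sets the target: "We aim to randomize 100 participants over 13 months into the trial". Section 2.4 describes the two arms as "65 participants in the SCRIPT intervention arm and 35 participants in the standard of care arm". Section 3.1 shows where the 65 comes from: "three ACT sessions over one month in approximately 13 groups of 5 people each (n=65". Section 3.3.A also gives the group size as about five.

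Section 3.2 describes the allocation: "Randomization is not stratified by any factor"; "We generated a random sequence of 34 blocks, sizes 3 and 6"; "Then, we randomized assignments within each block with an allocation ratio of 2:1". It adds that more blocks were made than needed, in case enrolment runs past the planned number.

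Section 4.5 says when a group begins: the first session "will occur once five participants have been randomized into the intervention group" and all five can attend. Under the missed-visits heading at the end of section 4.6, someone who misses session 1 is moved to a later group. Section 3.5.A times ACT follow-up from the first group session and control follow-up from baseline, and says the windows only guide scheduling. Sections 8 and 8.1 commit to intention-to-treat analysis by randomised arm, allowing for correlation within groups.

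**The concern.** A ratio of 65 to 35 is 1.86:1, not 2:1. Blocks of 3 and 6 hold the running allocation close to 2:1, so the discrepancy cannot be put down to chance: at exactly 100 randomised, 65 ACT participants is impossible. Two sections of one document therefore describe different allocations.

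There is also an operational worry. Once 13 groups of exactly five have been filled, one to three ACT participants remain. If a group may start only when five are available, and enrolment has stopped, those people would have no group. ACT follow-up visits are counted from the first session, so they would have no follow-up date either. They would lower the participation figure and could drop out of the stigma comparison. If that chain held, it would touch a feasibility outcome and the completeness of the primary comparison.

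**Working it through.** **Inputs.** N = 100 (section 2.9); 65:35 (2.4); about 13 groups of five (3.1); group size about five (3.3.A); 2:1 within blocks of 3 (2 ACT, 1 control) and 6 (4 ACT, 2 control), unstratified (3.2). The mix of block sizes is not given, so it is varied below.

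**1. The plan's own figure.** 13 x 5 = 65 and 100 − 65 = 35. The stated split reproduces exactly as a group count. 65/35 = 1.857.

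**2. Expectation under 2:1.** 100 x 2/3 = 66.67 ACT and 33.33 control. The stated 65 is 1.67 low.

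**3. Possible counts at exactly 100.** There is one sequence, so only one block can be incomplete.
- Complete blocks end at 99: 66 ACT, and the next slot adds 0 or 1, giving 66 or 67.
- Complete blocks end at 96 and a block of 6 is open with four slots used: 64 ACT plus 2, 3 or 4, giving 66, 67 or 68.

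Control is then 34, 33 or 32. A count of 65 has probability zero.

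**4. Probabilities,** by share of blocks that are size 3:

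| Share of size 3 | 66 ACT | 67 ACT | 68 ACT |
|---|---|---|---|
| 0.25 | 0.362 | 0.610 | 0.029 |
| 0.50 | 0.356 | 0.622 | 0.022 |
| 0.75 | 0.347 | 0.640 | 0.013 |

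The mean is 66.67 in each case.

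**5. Fit into 13 groups.**
- 66 = 12 x 5 + 1 x 6, mean size 66/13 = 5.08
- 67 = 11 x 5 + 2 x 6, mean size 67/13 = 5.15
- 68 = 10 x 5 + 3 x 6, mean size 68/13 = 5.23

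Each of these is 13 groups of about five, as the plan describes. A fourteenth group is not required.

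**6. Precision.** For a difference in means with a common standard deviation, the standard error is proportional to √(1/n₁ + 1/n₂).
- 65:35 gives 0.2097
- 66:34 gives 0.2111 (0.7% higher)
- 67:33 gives 0.2127 (1.4% higher)
- 68:32 gives 0.2144 (2.2% higher)

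Allowing for clustering in 13 roughly equal ACT groups with intra-group correlation ρ, the variance is proportional to (1 − ρ)/n₁ + ρ/13 + 1/n₂. The documents give no ρ, so take 0 to 0.2 as an assumed range. At ρ = 0.2:
- 65:35 gives 0.8/65 + 0.2/13 + 1/35 = 0.0563
- 67:33 gives 0.8/67 + 0.2/13 + 1/33 = 0.0576

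The standard error rises by about 1.2%, against 1.4% at ρ = 0. Clustering does not enlarge the effect.

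**7. Dependence on stopping at exactly 100.** At 99 randomised, with complete blocks ending at 96 and three slots of a block of 6 used, ACT is 64 plus 1, 2 or 3. A count of 65 is then attainable. One hundred is a target, and section 3.2 foresees going past it.

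**The case for a change.** The strongest reply is that the allowance for approximation covers the groups only. Section 2.4 states the arm sizes without any qualifier, and they are the only planned per-arm numbers in the document. That is correct, and the mismatch of one to three people is real.

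The reply on group formation is also fair. The 66th to 68th ACT participants are randomised after the 65th, when a thirteenth group may already have begun, and no rule says how to place late arrivals. At even accrual, about 67 ACT participants over 13 months is 67/13 ≈ 5.2 a month, or one roughly every six days. The session 1 window closes 31 days after baseline, so there is little room to hold the last group open.

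This does not lead to untreated or lost participants. Five is a trigger for starting a group; nothing makes it a ceiling, so any earlier group can take a sixth member. Moving people who miss session 1 into later groups already means that groups will not be exact sets of five. Windows are guides, and intention-to-treat keeps everyone in the assigned arm. It is true that an ACT participant who never attends a first session has no defined follow-up anchor. That applies to any such participant at any arm size. It is a separate matter and does not arise from 65 versus 67.

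**Conclusion.** The count stands: with exactly 100 randomised in 2:1 blocks of 3 and 6, the ACT arm has 66 to 68 people and control 32 to 34, so 65:35 cannot occur exactly. The stronger claims do not stand. Thirteen groups of about five hold everyone, and no passage leaves a randomised participant without a group or outside the analysis.

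The mismatch is one to three people in a planning number that no stated power calculation or analysis uses. Its cost in standard error is about 1.4% at the most likely split and 2.2% at the extreme. The allocation that governs the trial is the generated 2:1 sequence, and the analysis will use the numbers actually randomised. Describing the split as 2:1, or as roughly 65:35, would be tidier, but no result would differ.

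This rests on two assumptions: that staff use the stated flexibility in group size to place a few extra people, and that the precision comparison uses a common standard deviation and 13 roughly equal ACT groups. No change to the plan follows.
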